Secondary per-protocol analysis expanded to also be performed for safety outcome of graft survival	Primary analysis remains intention-to-treat but per-protocol analysis may be useful to demonstrate true effect of receiving agent on safety.	Statistical methods
Modified analysis of time-to-event outcomes to utilize Cox regression	This approach allows adjustment for covariates in constructing Hazard Ratios	Statistical methods
Count outcome data (i.e. number of organs transplanted) will be analyzed using generalized estimating equations	This is a more flexible approach than pre-specifying Poisson model for comparison of groups	Statistical methods
Better outline the process of safeguarding recipients as human subjects, including basis for waiver of recipient consent and monitoring for any safety concerns (e.g. interim analysis, oversight by DSMC)	Recipients are human subjects and it is important to clearly delineate how their privacy and health is protected in this trial	Ethics approval and consent to participate

Protocol Summary

Title:	A Multicenter Randomized Placebo-Controlled Trial of Intravenous Thyroxine for Heart-Eligible Brain Dead Organ Donors
Precis:	This randomized non-blinded study will compare intravenous thyroxine (T4) to saline placebo in 800 brain dead organ donors who have provided authorization for research and are eligible for heart transplantation based on age and lack of exclusions
Objectives	
Primary: Intravenous thyroxine (T4) will increase the proportion of hearts transplanted when given early after brain death to heart-eligible hemodynamically unstable potential organ donors
 
Safety: Hearts transplanted from donors receiving T4 will have non-inferior 30-day graft survival to those from the placebo group
 
Secondary: T4 will reduce time to wean off vasopressors and improve cardiac ejection fraction

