Our next study aimed to test whether T4 infusion would be superior to placebo in heart-eligible donors with reduced LVEF despite being off vasopressors. Both studies aimed to enroll and start infusion within 12 hours of BD (at least defined by time when declaration occurred). Neither studies were blinded but evaluation of LVEF was performed blind to treatment allocation. Median improvement in LVEF was 10% with T4 compared with 5% without thyroid hormone ($p=0.24$), although intention-to-treat efficacy analysis was limited by the fact that several of those randomized to T4 either did not receive or had this intervention discontinued prematurely due to emergent hypertension or tachycardia (14). There was a trend to more hearts being transplanted in the T4 group (59 vs. 27%, $p=0.14$) as well as more organs in total transplanted per donor (median of 5 vs. 3, $p=0.009$). Although this study suggested that thyroid hormone could be efficacious in increasing hearts transplanted, definitive conclusions were precluded by its small sample size (a consequence of enrolling at only one OPO) and group imbalances despite randomization. Therefore, we believe that there remains scientific equipoise and significant interest amongst the OPO and transplant communities in determining whether thyroid hormone does actually improve heart function and result in more

hearts transplanted.

In fact, scientific research to determine the optimal interventions for donor management have been receiving increasing interest (15). To date, most studies have been retrospective and not adequately controlled (16, 17). Recently, OPOs have begun collaborating more intently to answer important donor management questions. A council focused on research was formed as part of the *Association of Organ Procurement Organizations* (AOPO). This Organ Donation Research Council (ODRC) aims to bring together OPOs and interested parties (such as transplant physicians and scientists) to advance the science of organ and tissue donation. Collaborations nurtured as part of ODRC led to a multi-center randomized study that demonstrated that naloxone, frequently used (based on retrospective studies) to improve lung function, did not actually improve oxygenation or result in more lungs transplanted than a saline placebo (18). A few other randomized donor management studies have been performed (19-21).

Objectives {7}

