8. Other reason preventing donor from receiving study drug (determined by on-site coordinator)

* sufficient to exclude donor heart from being considered for transplantation

Who will take informed consent? {26a}

Donors are dead and their surrogates have all provided authorization for research. This is verified by organ procurement coordinators who are managing the donor management process. Recipients of organs from those enrolled in this study are human subjects but we have obtained a waiver of consent to collect de-identified graft function/outcome data on those receiving hearts from donors enrolled in this trial.

Additional consent provisions for collection and use of participant data and biological specimens {26b}

All data utilized for analysis will be collected as part of donor care including standard UNOS and SRTR data variables (e.g. demographics). No additional biologic specimens will be collected.

Interventions

Explanation for the choice of comparators {6b}

Intravenous thyroxine (T4) is commonly employed at almost all OPOs around the country as part of standard hormonal resuscitation, either for all donors or only those who are hemodynamically unstable (8). It is recommended (without level I evidence) in several donor management guidelines (22). It is usually given as an infusion with or without an initial bolus (protocols vary). A pilot randomized comparison of thyroid hormone formulations (T3 vs. T4) did not suggest any important benefits of T3 over T4 (12). Treatment with T4 will be compared to no thyroid hormone (during the first twelve hours, open-label T4 may be used after).

Intervention description {11a}

Study infusion (saline or thyroxine) will be commenced as soon as possible after randomization. Serum free T4 and TSH levels will be drawn prior to giving the drug. The T4 will be prepared by mixing 500 μ g of drug in

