500-ml of normal saline (i.e. concentration of 1 μ g/ml) and enclosing the bag in an opaque sleeve. The placebo will be a 500-ml bag of normal saline (without active drug) also enclosed in an opaque sleeve. The infusion from this bag will be started at 30 ml/hour (corresponding to 30 μ g/hour) and run for at least 12 hours, unless adverse effects occur and the infusion is stopped prematurely (see titration protocol below). Vasoactive medications will be weaned as expeditiously as possible. When the donor is considered hemodynamically stable, initial transthoracic echocardiography (TTE) will be ordered and obtained as soon as possible. Repeat serum free T4 level should be drawn prior to organ recovery in both groups. Organ allocation will proceed per OPTN policy and routine allocation practices. All other aspects of donor management will also follow local OPO protocols.

Criteria for discontinuing or modifying allocated interventions {11b}

Titration protocol: T4 can be titrated down if:

- a) Systolic Blood Pressure above 180 mm Hg and increase of 30 mm Hg above baseline
- b) Heart rate over 120 bpm and increase by 20 bpm above baseline
- c) New tachyarrhythmia (atrial fibrillation, atrial flutter, supraventricular tachycardia, ventricular tachycardia) or new onset ectopy (ventricular premature contractions > 6/min)
- d) Other significant change, at discretion of the coordinator

The dose should be reduced in increments of 10 μ g/hour (i.e. to 20 then 10 μ g/hour). The infusion can be discontinued if hemodynamic instability persists despite weaning.

Open-label T4 can be given to the placebo group after 12-hours at the discretion of the managing team (whether for persistent hemodynamic instability, low EF on echo, or physician preference). T4 can also be continued beyond 12-hours of study infusion for the same reasons in the intervention group.

Strategies to improve adherence to interventions {11c}

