level of 0.025. We will also present the effect size with confidence intervals for all outcomes. The analysis will follow an intention-to-treat model. However, we will also perform a secondary per-protocol analysis, including only those receiving at least six hours of study infusion. We will also analyze only those in the placebo group who did not receive open-label T4, for a secondary analysis.

We will analyze the primary safety endpoint of recipient graft survival using a non-inferiority method. Our baseline assumption, based on five-year data (from 2016 to 2020) provided by SRTR, is that 30-day graft survival for hearts will be 96%. We assume this baseline rate for both study groups, as there is no evidence to suggest that graft survival is lower in recipients of hearts from donors administered thyroid hormone. In fact, a recent study suggested treatment was associated with improved graft survival (23). The null hypothesis is that heart graft survival is lower in the T4 treated group by at least a clinically significant margin (set at 6%) compared with that observed in hearts transplanted from the placebo donors. This non-inferiority margin was selected with input of the data and safety monitoring committee (DSMC), including a thoracic transplant surgeon and ethicist. It aligns with that used in other trials assessing graft function after heart transplantation which used similar baseline assumptions (96% graft survival) but allowed more liberal margins (10%) (26). We believe that setting the lower limit of tolerance for this safety analysis at 90% graft survival is most appropriate. We will construct two-sided 95% confidence intervals for the difference in graft survival between the groups, allowing us to test for one-sided non-inferiority at alpha 0.025. This will be performed in the intention-to-treat cohort (i.e. all hearts from enrolled donors, by randomized study group) but we will also evaluate non-inferiority using a per-protocol methodology (i.e. evaluating outcomes in recipients who received hearts from donors who received at least six hours of T4 infusion compared to those who did not).

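### The graft-survival per-protocol analysis is written as an as-treated split, and the EF subgroup appears to use a post-randomisation measurement

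*Combined protocol and SAP*

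**What the plan says.** Section {20a} makes intention-to-treat the main analysis for hearts transplanted and for graft survival. It then describes a per-protocol analysis twice.

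- General rule: "including only those receiving at least six hours of study infusion". Section {11a} shows that study infusion covers both arms: "Study infusion (saline or thyroxine) will be commenced as soon as possible after randomization". The rule is symmetric and drops short infusions.
- Graft-survival rule: non-inferiority is also to be evaluated by comparing "hearts from donors who received at least six hours of T4 infusion compared to those who did not". Neither randomised arm nor exclusion is mentioned.

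The version 3.0 amendment table presents the second analysis as an expansion of the first, and gives as its reason that "per-protocol analysis may be useful to demonstrate true effect of receiving agent on safety". Section {20c} adds that later analyses may leave out donors not managed according to the protocol, without defining them.

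On who changes group, {11a} has the infusion run at least 12 hours "unless adverse effects occur and the infusion is stopped prematurely". In the pilot described in {6a}, several T4 donors did not receive T4 or "had this intervention discontinued prematurely due to emergent hypertension or tachycardia". Section {11b} states: "Open-label T4 can be given to the placebo group after 12-hours at the discretion of the managing team". The reasons it accepts for doing so are unresolved instability, a poor EF, or simply what the physician prefers.

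Section {20b} lists a subgroup by EF result, above 50% versus 50% or below, and does not say which echocardiogram supplies it.

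**The concern.** The two per-protocol rules define different comparisons. The first keeps randomised arms and removes short infusions. The second removes no one and sorts hearts by the T4 the donor received. Neither kind of move between groups is random. T4 infusions are cut short for adverse effects, and open-label T4 goes to placebo donors partly because they are unstable or have a low EF.

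The bias can run either way. Early-stopped T4 hearts in the comparator can hide harm from T4. Sicker placebo donors counted on the T4 side can create apparent harm where none exists. This matters because the plan will judge non-inferiority of its primary safety endpoint in this set as well.

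The EF subgroup raises a related problem. If the EF is measured after T4 has started, stratifying on it removes part of the pathway through which T4 is meant to increase transplantation.

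**Working it through.** **The plan's own figures.** With 96% survival in both arms, a 6-point margin and one-sided alpha 0.025, n per arm = (1.960 + 0.842)² × 2 × 0.96 × 0.04 / 0.06² = 167.4, so 168 (336 in total), as stated in {14}. With 160 per arm the standard error is √(0.0768/160) = 0.0219, and power is Φ(0.06/0.0219 − 1.960) = 78%, also as stated. Neither figure is disputed.

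**Graft survival: inputs.** From the documents: 96% survival, the 6-point margin, and 160 hearts per arm (320 split equally). Assumed, because the documents give no values: f, the share of T4-arm hearts with under six hours of T4; s, survival in those hearts; c, the share of placebo hearts with six or more hours of open-label T4; q, survival in those hearts. Survival elsewhere is 96%.

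- ITT difference = [(1−f)·0.96 + f·s] − [(1−c)·0.96 + c·q]
- As-treated difference = [(1−f)·0.96 + c·q]/(1−f+c) − [f·s + (1−c)·0.96]/(1+f−c)

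Probabilities are exact binomial. Non-inferiority is declared when the lower Wald 95% limit exceeds −6 points.

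*(a) Harm confined to early stoppers, no crossover.* For f = 0.15 and s = 0.80: ITT = 0.816 + 0.120 − 0.960 = −2.4 points; as-treated = 0.960 − (0.120 + 0.960)/1.15 = +2.1 points.

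| f | s | ITT, points | ITT, P(non-inferior) | As-treated, points | As-treated, P(non-inferior) |
|---|---|---|---|---|---|
| 0.05 | 0.90 | −0.3 | 73% | +0.3 | 80% |
| 0.05 | 0.86 | −0.5 | 69% | +0.5 | 82% |
| 0.10 | 0.91 | −0.5 | 69% | +0.5 | 82% |
| 0.20 | 0.86 | −2.0 | 39% | +1.7 | 88% |
| 0.15 | 0.80 | −2.4 | 32% | +2.1 | 90% |

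*(b) Last row of (a) plus crossover, c = 0.30.* As q falls through 0.96, 0.90, 0.85 and 0.80, as-treated gives +2.8, +1.3, −0.05 and −1.4 points. ITT gives −2.4, −0.6, +0.9 and +2.4.

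*(c) No treatment effect, same prognosis in both arms.* A share h of donors is high-risk with survival r, and the rest have (0.96 − h·r)/(1−h). All high-risk placebo donors get six or more hours of open-label T4, and 24 of 160 T4 donors (15%) stop at random. For h = 0.30 and r = 0.91 the rest have 98.1%. The T4 side is (136 × 0.96 + 48 × 0.91)/184 = 94.7%, the comparator (112 × 0.981 + 24 × 0.96)/136 = 97.8%, a false deficit of 3.1 points. Over h = 0.15–0.30 and r = 0.91–0.93, as-treated shows −0.9 to −3.1 points, and the chance of declaring non-inferiority falls from 65% to 32%. ITT shows 0.0 and 78%. A set that keeps randomised arms and drops the 24 stoppers (136 versus 160) shows 0.0 and 73%.

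*(d) T4 truly 6 points worse throughout (90% versus 96%), stopping unrelated to outcome, no crossover.* False non-inferiority under as-treated is 4.1%, 5.1%, 5.75% and 7.2% for f = 0.05, 0.10, 0.15 and 0.20. ITT gives 3.1%. For f from 0.10 to 0.20 the arm-preserving set gives 3.4–3.5%.

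**EF subgroup: timing.** Section {11a} orders the initial echocardiogram once the donor is stable, after describing the start of the infusion. In {12}, time to stability adequate for ordering it is a secondary outcome, and so is the EF it yields. The EF model in {20a} has no baseline EF, whereas the vasopressor-inotrope score (VIS) analysis has a baseline score. No inclusion criterion requires an echocardiogram. Together these point to a post-infusion EF.

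**EF subgroup: size.** The 35% control rate is from {14}; the rest is assumed. Control EF is normal with (mean, SD) = (48, 12), (45, 10), (52, 12) or (55, 10). T4 adds 3 or 5 EF points. Logit P(transplant) = a + b(EF − 50), with b = 0.05, 0.07 or 0.09 and a set to give 35%.

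- T4 acting only through EF: a true overall gain of 3.2 to 9.2 points appears as 1.1 to 5.7 in the stratum above 50% and 0.6 to 3.1 in the other.
- T4 raising EF without changing transplantation: the strata show −1.6 to −7.4 and −1.7 to −4.8 points, although the true effect is zero.

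**The case against.** The strongest reply is that the graft-survival clause is loose shorthand. The amendment table calls the analysis an expansion of the existing per-protocol analysis, and {20c} speaks of excluding cases, not moving them. On that reading the comparator is simply the placebo side of the six-hour set, and one clarifying sentence suffices. That intention is plausible, but the operative sentence does not say it. The stated aim of isolating the effect of receiving the agent points towards exposure. If that was meant, the label is wrong. The text needs correcting on either reading.

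Second, cases (b) and (c) need open-label T4 to count as T4 infusion, although the protocol names it separately and gives it no duration. Case (c) also moves every high-risk placebo donor. Both points stand, so these cases show direction and possible size, not expected size.

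Third, nothing in the documents links donor hypertension or tachycardia to recipient graft loss, and {11b} provides for dose reduction before discontinuation. With 5% stoppers at 86–90% survival, the as-treated difference is only +0.3 to +0.5 points. That stands as the low end.

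Fourth, the EF time point is unstated, the data forms were not available, and the valve exclusion in {10} mentions echocardiography, so some donors may have an earlier one. The post-infusion reading is therefore an inference, though the natural one.

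**Conclusion.** The concern holds. The graft-survival rule conflicts with the six-hour rule given shortly before it and, as written, is an as-treated comparison under a per-protocol label. This does not depend on any scenario. The size does: under the assumptions shown, the as-treated difference ranges from about +2.8 to −3.1 points against a 6-point margin, and it can have the opposite sign to ITT. With few early stoppers and no crossover the distortion is about half a point or less.

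The EF subgroup appears to condition on a post-randomisation outcome. If so, its stratum effects can be well below a true benefit or show harm that does not exist.

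Both issues touch supportive analyses only. They should be corrected before the data are analysed, but they do not threaten the trial's main conclusions.

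**What to change.** **Graft survival.** Keep every heart in its donor's randomised arm and apply the rule already used for hearts transplanted: at least six hours of study infusion, saline or T4. Tie the {20c} exclusions to that rule. If the exposure question is wanted, add it separately, labelled as-treated and exploratory, and state how open-label T4 is counted. The corrected set is still selected after randomisation, so it remains supportive to ITT.

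**EF.** Report EF as an outcome and remove it as a treatment-effect subgroup, unless a pre-infusion EF is meant, in which case specify it. If a severity subgroup is wanted, a pre-infusion variable such as baseline VIS is one option.

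**Cost.** Wording in {20a} to {20c} and little programming. The arm-preserving set cannot show harm confined to early-stopped hearts: it gives 0.0 throughout case (a), where ITT shows −0.3 to −2.4 points. It is also smaller, with a 73% rather than 78% chance of declaring non-inferiority when 15% of T4 donors stop and there is no true difference. The EF-stratified comparison would be lost, and baseline VIS answers a somewhat different question.

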Endpoints	
The primary outcome is the proportion of hearts transplanted (the number of hearts transplanted divided by the total number of potential donors).
 
The safety outcome is proportion of hearts transplanted that maintain graft function at 30-days and 1-year.
 
Secondary outcomes will include: 1) time from randomization to weaning off vasopressors: defined as being off all vasoactive agents (except for vasopressin); 2) proportion weaned off vasopressors by 12-hours (same criteria as #1); 3) time achieving hemodynamic stability adequate to order first echocardiograph; 4) left ventricular ejection fraction measured on first donor echocardiography; 5) total number of organs transplanted

Population	We plan on enrolling 800 brain dead organ donors with authorization for donation and research in order to have 752 evaluable subjects who receive the study drug or placebo
Phase	Three
Number of Sites	Est. 14 OPOs, 1 coordinating site for human (recipient) data
Study Duration	18-24 months

Abbreviations

AOPO, Association of Organ Procurement Organizations

BD, brain dead

DSMC, data and safety monitoring committee

LVEF, left ventricular ejection fraction

OPO, organ procurement organization

ODRC, Organ Donation Research Council

OPTN, Organ Procurement and Transplant Network

SRTR, Scientific Registry of Transplant Recipients

T4, thyroxine

TTE, transthoracic echocardiography

UNOS, United Network for Organ Sharing

Administrative information

Title {1}	A Multicenter Randomized Placebo-Controlled Trial of Intravenous Thyroxine for Heart-Eligible Brain Dead Organ Donors
Trial registration {2a and 2b}.	Clinicaltrials.gov NCT04415658. Registered June 4, 2020. https://clinicaltrials.gov/ct2/show/NCT04415658
Protocol version {3}	3.0
Funding {4}	None (internal administrative support provided by Mid-America Transplant)
Author details {5a}	[name], Washington University in St. Louis School of Medicine [name], Mid-America Transplant
Name and contact information for the trial sponsor {5b}	Mid-America Transplant [name]
Role of sponsor {5c}	Mid-America Transplant will not have any role in the design or analysis of the trial data. They will not have any role in the writing of the manuscript or the decision to submit the report for publication.

Introduction

Background and rationale {6a}

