There will be a one-month run-in period at each site where screening logs will be checked by the site and central study coordinators for completeness and accuracy. They will review all cases where donors were not enrolled within 24 hours or if other reasons for ineligibility were provided and provide feedback. The site and study coordinators will have weekly conference calls for the first month (and then monthly thereafter) to discuss issues with adherence. They will also provide feedback to individual OPO personnel if study protocols are violated. The study statistician will perform monthly audits of study data for completeness.

Relevant concomitant care permitted or prohibited during the trial {11d}

All standard OPO donor management practices will be continued throughout the study period until and including organ allocation and recovery. The only intervention prohibited is administration of thyroid hormone to those donors allocated to the placebo group for the first 12 hours after randomization.

Provisions for post-trial care {30}

Data collection on non-human organ donors ends at time of organ procurement or end of donor management (for authorized brain-dead potential donors who do not go on to donate organs).

Outcomes {12}

The primary outcome for this study is the proportion of hearts transplanted (the number of hearts transplanted divided by the total number of potential donors – including those authorized but not recovered).

The primary safety outcome for this study is 30-day graft survival in those receiving hearts from those enrolled in this study. This is defined by patient survival with the originally transplanted heart and no mechanical circulatory support. It will be assessed primarily at 30-days but also at 1-year.

Secondary outcomes will include:

1. Time from randomization to weaning off vasopressors: defined as being off all vasoactive agents, except for vasopressin (≤ 1 U/hr)
2. Proportion weaned off vasopressors by 12-hours (same criteria as #1)
3. Vasopressor-inotrope score at 12-hours (excluding vasopressin ≤ 1 unit/hour)
4. Time achieving hemodynamic stability adequate to order first echocardiography
5. Ejection fraction measured on first donor echocardiography
6. Lungs and total thoracic organs transplanted
7. Total number of organs transplanted

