Our plans for analyzing the secondary outcomes are as follows: for outcome measures that are time-to-event variables such as time to get off vasopressors and time to order first echo, we will perform Cox regression model to assess Hazard Ratio (95% confidence interval) between groups. We will calculate the vasopressor-inotrope score, VIS (27) as: $VIS = \text{dopamine dose } (\mu\text{g/kg/min}) + \text{dobutamine dose } (\mu\text{g/kg/min}) + 100 \times \text{epinephrine dose } (\mu\text{g/kg/min}) + 100 \times \text{norepinephrine dose } (\mu\text{g/kg/min}) + 10 \times \text{milrinone dose } (\mu\text{g/kg/min}) + 100 \times \text{phenylephrine dose } (\mu\text{g/kg/min}) + 10,000 \times \text{vasopressin dose } (\text{U/kg/min} - \text{only for doses } > 1 \text{ U/hour})$. We will compare the decrease in VIS from start of thyroid hormone or saline infusion until 12-hours (end of study infusion), using analysis of covariate method with predictor variables that include the baseline score and the treatment groups and adjusting for site effect. Cardiac ejection fraction will be evaluated using a linear mixed model adjusting for random site effect. If normality assumption is violated, data transformation will be performed. Count data regarding thoracic and total organs transplanted will be compared using Generalized Estimating Equations, with study group as the independent variable and expected organs transplanted as a covariate. All secondary outcome analyses will be two-tailed test at a significance level of 0.05.

Interim analyses {21b}

The DSMC statistician will perform one interim analysis when 376 donors have been enrolled with evaluable data. The trial may be terminated early if, based on the judgement of the DSMC, the interim findings

demonstrate either superiority or clear inferiority of T4 treatment compared to placebo (at a threshold of 0.01). The trial may also be terminated if there is inferiority of graft outcomes in either group, observed at 30-days in those hearts transplanted and observed for this period. The DSMC will provide recommendations to the study PIs, who will make final decisions about whether to stop or continue the trial.

Methods for additional analyses (e.g. subgroup analyses) {20b}

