We will analyze the primary outcome (proportion of hearts donated) for each OPO individually. Sample sizes will vary between OPOs, so we may only have power to detect large effect sizes. Still, these OPO-specific analyses could provide valuable insights about trends at each OPO.

We will perform prespecified subgroup analyses of:

1. Time to start < 12 hours vs. > 12 hours from BD determination
2. EF result (normal, > 50%, abnormal ≤ 50%)

Methods in analysis to handle protocol non-adherence and any statistical methods to handle missing data {20c}

Donors who are not managed according to the protocol (e.g., not managed properly on T4) will be included in the initial analyses following an intent-to-treat model. Subsequent analyses may exclude those cases in order to evaluate the impact of the protocol on donors who completed it successfully.

Plans to give access to the full protocol, participant level-data and statistical code {31c}

The participant-level (donor) dataset will be made available to all study investigators and their respective OPOs. It may be provided to other OPOs, on request. No recipient outcome data will be shared.

Oversight and monitoring

Composition of the coordinating center and trial steering committee {5d}

The coordinating center is comprised of the study PIs and the central study statistician. The coordinating center will be responsible for oversight of the study. The study statistician will review data entered by study sites for completeness and perform periodic checks for accuracy. The central study coordinator will ensure transfer of additional donor-related data and demographics for each enrolled donor to the central database on a quarterly basis. The respective study OPOs will provide donor data only and not be involved in collecting or analyzing recipient data.

Composition of the data monitoring committee, its role and reporting structure {21a}

The data and safety monitoring committee (DSMC) will be composed of several experienced but independent transplant researchers covering a wide range of expertise.

DSMC Member	Expertise	Institutional Affiliation
[name], PhD CHAIR	Transplant Physician and Researcher SRTR senior scientist	Professor of Medicine with tenure, Co-director of Clinical Research, Medical Director of Living Donation, SSM Health Saint Louis University Transplant Center
[name]	Thoracic Transplant Surgeon (Pediatrics)	Assistant Professor, Department of Surgery, University of Cincinnati

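### The time-to-start subgroup and the vasopressor-score change both depend on infusion start, a post-randomization event that some randomized donors may not have; both can be tied to randomization instead

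*Combined protocol and SAP*

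**What the plan says.** All references are to the combined protocol and SAP, version 3.0.

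- **VIS change.** Statistical methods {20a}: "We will compare the decrease in VIS from start of thyroid hormone or saline infusion until 12-hours". A parenthesis there equates that time with the end of study infusion. The analysis is a covariance model with "predictor variables that include the baseline score and the treatment groups and adjusting for site effect". Outcomes {12} lists the same score at 12 hours and names no origin for the clock.
- **Subgroup.** Additional analyses {20b}: "Time to start < 12 hours vs. > 12 hours from BD determination". The interval begins at brain death determination and ends at infusion start.
- **Clocks that run from randomization.** Outcomes {12}, secondary outcome 1: "Time from randomization to weaning off vasopressors". Concomitant care {11d} bars thyroid hormone in the placebo group "for the first 12 hours after randomization".
- **Open-label T4.** Sections {6b}, {11b} and {17b} allow it once a 12-hour period is over, without saying when that period begins.
- **Start and length of infusion.** Section {11a} asks for a prompt start after randomization but sets no limit on the delay. Twelve hours is a minimum duration, and the infusion may stop early for adverse effects.
- **Analysis set.** Sections {18b} and {20a} follow intention-to-treat, and {18b} keeps donors assigned to T4 who never receive it. The only imputation rule there concerns heart transplantation.
- **Allowance for loss.** The Protocol Summary (Population) plans 800 enrolled "in order to have 752 evaluable subjects who receive the study drug or placebo".

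**The concern.** An analysis of donors as randomized needs a time zero and a subgroup label that every randomized donor has. Infusion start supplies neither for a donor who is never infused. Such a donor's primary outcome is still known or imputed under {18b}, yet the donor cannot be placed in either time-to-start subgroup.

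Staff know the allocation before they start the infusion, so the time of starting, and whether it starts at all, is not protected by randomization in the way a baseline variable is. A comparison within subgroups formed by it is not strictly a randomized comparison.

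For VIS there is a second issue. If the thyroid hormone ban runs from randomization while the score is read 12 hours after infusion start, some placebo donors could be scored when open-label T4 is already permitted. That could narrow the contrast between the groups.

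**Working it through.** **1. The plan's own figure.** Sample size {14} gives 35% vs 45%, 80% power and one-sided alpha 0.025. With pooled variance and no continuity correction:

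n per group = [1.960 × √(2 × 0.40 × 0.60) + 0.842 × √(0.35 × 0.65 + 0.45 × 0.55)]² / 0.10²
= [1.358 + 0.580]² / 0.01 ≈ 375.6, rounded up to 376, or 752 in total.

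This matches the plan. It concerns the primary outcome only; the documents give no sample size for VIS or for the subgroup.

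**2. Bound on donors who never start.** 800 − 752 = 48, and 48 / 800 = 6.0%. The Protocol Summary ties the 752 to receipt of study drug or placebo. Sample size {14} attributes the loss to clinical issues that interrupt adherence, which also covers donors who start and then stop. The number of non-starters within this allowance is therefore anywhere from 0 to 48.

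**3. What each definition yields.**

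| Donor | VIS change as written | Subgroup as written | Subgroup from brain death to randomization, ≤12 vs >12 h |
|---|---|---|---|
| Infused | defined if scored | defined, unless the start is at exactly 12 h | defined |
| Never infused | no time zero | no category | defined |

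**4. Subgroup crossing.** A donor randomized at or before 12 hours from brain death is counted as late if the time to randomization plus the start delay exceeds 12 hours. With an assumed delay of 1 hour, everyone randomized after hour 11 and up to hour 12 crosses over.

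**5. Overlap with the open-label period.** Let d be the delay from randomization to infusion start. A score read 12 hours after infusion start falls at d + 12 hours after randomization. Under {11d} the ban ends at 12 hours, so the overlap is (d + 12) − 12 = d. The documents give no value for d; those below are assumptions.

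| d (h) | VIS read, hours after randomization | Overlap under {11d} (h) | Overlap if the 12 hours are infusion time (h) |
|---|---|---|---|
| 0.25 | 12.25 | 0.25 | 0 |
| 0.5 | 12.5 | 0.5 | 0 |
| 1 | 13 | 1 | 0 |
| 2 | 14 | 2 | 0 |
| 4 | 16 | 4 | 0 |

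A score read 12 hours after randomization has no overlap under {11d}, whatever the delay.

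**The case against.** The best defence is that the plan already keeps non-adherent donors in their assigned group ({18b}, {20c}). Outcomes {12} lists VIS at 12 hours without an infusion origin, so a donor who was never infused may still have a usable score. The start is meant to be prompt, so any delay may be short. Open-label T4 is discretionary, so permitted does not mean given, and {20a} plans a secondary analysis limited to placebo donors who did not receive it. Measuring from infusion start also matches exposure to the drug. Much of this stands, and it keeps the point small. It does not say what VIS change or subgroup a never-started donor receives, and the open-label analysis is not tied to VIS.

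A reader might infer more than the documents support:

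- *That 48 donors will never be infused.* The 48 is a ceiling; no section forecasts it as the number of non-starters.
- *That the pilot shows how often this happens.* The Introduction groups donors who did not receive T4 with those who stopped early, and gives no split. Early stoppers do have a start time. That pilot also enrolled donors off vasopressors, unlike this trial.
- *That non-starting will differ by group because T4 has to be mixed.* Nothing in {11a} says that mixing prevents a start. Dependence on group is possible in an unblinded trial but is not shown.
- *That the 12-hour VIS is contaminated by open-label T4.* This depends on reading the period from randomization as in {11d}, on a delay that is not given, and on actual use.

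**Conclusion.** The point holds as a minor one. The subgroup depends on a post-randomization event, leaves never-started donors uncategorized and assigns exactly 12 hours to neither side. The VIS change has no defined value for never-started donors, although the plan analyses donors as randomized. At most 6% of donors (0 to 48 of 800) are affected in this way, taking the plan's enrolment allowance as the ceiling. The overlap with the open-label period equals the start delay under {11d} and is zero if the 12 hours are infusion time; its actual size cannot be derived from the documents. The case for change is clearest for the subgroup, where a baseline alternative is already available. A reader might take this as a threat to the main result. It is not: one secondary outcome and one subgroup definition are involved, and the primary test and its sample size stand.

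**What to change.** 1. **Subgroup.** Define it by time from brain death determination to randomization, ≤12 vs >12 hours. Section {16b} already logs the date and time of enrolment at allocation, and the time of brain death is needed for the first exclusion criterion in {10}.
2. **VIS.** Take baseline as the last score at or before randomization and the 12-hour value as the score nearest 12 hours after randomization. Include all randomized donors with a recorded score, infused or not. Keep the infusion-anchored change as a sensitivity analysis.
3. **Missing scores.** State how donors lost before 12 hours are handled; moving the clock does not solve that.
4. **Consistency.** Reconcile {6b}, {11a}, {11b}, {11d}, {17b} and {20a} on when the 12-hour period starts and whether it coincides with the end of infusion. Which clinical rule applies is for the investigators; this review takes no position on it.

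Cost: for the subgroup, SAP wording only. For VIS, the cost depends on when the vasoactive doses are recorded. No section available here shows a score at randomization or 12 hours later, and recruitment began on 01 December 2020. The recorded times may therefore not match the randomization clock exactly, and the nearest recorded value may have to serve. The sample size does not change.
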